2.4.3 Treatment Plan

The following table ([Table 2-1](#)) displays the distribution of patients, along with the respective dose and dosing interval. Patients enrolled under Amendments 07 and beyond are in addition to those enrolled under Amendment 06.

Table 2-1

Patient Distribution

	Amendment 001-02	Amendment 001-03/04	Amendment 001-05	Amendment 001-06	Amendment 001-07/08/09	Total N
Part A Dose Escalation	N=10 ¹					30 Solid Tumor
Part A-1	N=7 ¹					
Part A-2		N=13 (Q3W)				
Part B (MEL)	Ipilimumab naïve at 10 mg/kg (Q2W) ² N=41	Ipilimumab naïve at 10 mg/kg (Q3W) N=17				58
	Ipilimumab treated at 10 mg/kg (Q2W) ² N=16	Ipilimumab treated at 10 mg/kg (Q3W) N=26				42
		Ipilimumab naïve at 2 mg/kg (Q3W) N=22				22
			Ipilimumab refractory at 10 mg/kg (Q3W) N=25	Ipilimumab refractory at 10 mg/kg (Q3W) N=58		83
			Ipilimumab refractory at 2 mg/kg (Q3W) N=49	Ipilimumab refractory at 2 mg/kg (Q3W) N=41		90
					Ipilimumab naïve, or treated at 10 mg/kg Q2W or Q3W N=147	147

Patient Distribution (cont)

	Amendment 001-02	Amendment 001-03/04	Amendment 001-05	Amendment 001-06	Amendment 001-07/08/09	Total N
Part C (NSCLC)		10 mg/kg (Q3W) N=41				41
Part D (MEL)			Ipilimumab naïve at 2 mg/kg (Q3W) N=51			51
			Ipilimumab naïve at 10 mg/kg (Q3W) N=52			52
Part F-1 (NSCLC)				1L: 2 mg/kg (Q3W) N= 6	1L: 10 mg/kg (Q2W) N=47	53 ³
				1L: 10 mg/kg (Q3W) N= 5	1L: 10 mg/kg (Q3W) N= 45	50 ³
Part F-2 (NSCLC)				3L+: 10 mg/kg (Q3W) N=33		33 ³
					3L+: 10 mg/kg (Q2W) N=156	156 ⁴
					2L+: 10 mg/kg (Q3W) N=172	172 ³
					2L+: 10 mg/kg (Q2W) N=112	112 ³
Part F-3 (NSCLC)					2L+: 2 mg/kg (Q3W) N=55	55 ³

1L = First line arm

2L+ = Second line or greater arm

3L+ = Third line or greater arm

1 The dosing interval between Cycle 1 and Cycle 2 is 28 days, Cycle 2 and beyond will be repeated every 14 days

2 Patients in Part B are dosed Q2W. With Amendments 001-03, 001-04, 001-05, 001-06, or following approval of the administrative memo dated 06-Jan-2012, new patients are dosed Q3W

3 Patients' tumors express PD-L1

4 Patients tumors do not express PD-L1

Dose escalation in individual patients will not be permitted in this study, except as indicated for patients enrolled in Part A-2. In addition, for detailed guidelines for dose modifications, see Section 3.2.5.4.4.

The DETAILS portion of this document (Section 3) further outlines the treatment plan for the study, including permitted/prohibited medications and supportive care measures.

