(35 ipilimumab-naïve and 20 ipilimumab-treated) will be enrolled. With Amendment 05, 60 ipilimumab-refractory patients will be enrolled. The ipilimumab-naïve, ipilimumab-treated and ipilimumab-refractory cohorts are defined per eligibility criteria in Sections 2.2 and 2.3. With Amendment 06, the ipilimumab-refractory cohort will enroll an additional 100 patients for a total of 160 patients. The ipilimumab-refractory cohort will randomize up to 80 patients at 2 mg/kg and 80 patients at 10 mg/kg administered every 3 weeks (Q3W) who meet the ipilimumab-refractory eligibility criteria as provided in the current amendment in a 1:1 fashion, manually by the Sponsor, based on a computer-generated allocation schedule. Upon approval of Amendment 07, Part B will enroll an additional 230 patients irrespective of prior ipilimumab status. This cohort will randomize approximately 115 patients at 10 mg/kg Q2W and 115 patients at 10 mg/kg Q3W who meet the Part B eligibility criteria as provided in the current amendment in a 1:1 fashion, manually by the Sponsor, based on a computer-generated allocation schedule. If a patient is ipilimumab-refractory and BRAF V600E mutant, then one of the prior systemic treatment regimens must have included a vemurafenib, dabrafenib, or other approved BRAF or MEK inhibitors if allocated under Amendment 07. Ipilimumab naïve patients are allowed up to 2 prior systemic treatment regimens, one of which may have included prior treatment with a BRAF inhibitor.

In Part C, 35 patients with NSCLC may be enrolled (progressive metastatic or locally advanced NSCLC after treatment with two prior systemic regimens), and patients must have measurable disease (see Section 2.2 and Appendix 6.5). All patients will be dosed Q3W.

In Part D, patients with MEL may be enrolled (metastatic MEL or patients with locally advanced disease and not candidates for surgical resection or a definitive local therapy), and patients must have measurable disease (see Section 2.2 and Appendix 6.5). Part D will enroll approximately 88 patients, randomized 1:1 manually by the Sponsor based on a computer-generated allocation schedule, to either 2 mg/kg or 10 mg/kg. All patients will be dosed Q3W.

Enrollment in Part D will be restricted to ipilimumab-naïve patients who are allowed up to 2 prior systemic treatment regimens.

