3.5.7 Sample Size and Power Calculations

Part B ipilimumab-naïve enrolled through Amendment 4 (non-randomized)

With 61 ipilimumab-naïve patients treated at the 10 mg/kg in both Q2W and Q3W, the study has approximately 97% power to detect an effect size of RR=25% or DCR=50% under the null hypothesis of RR=10% and DCR=30%, or >99% power to detect an effect size of RR=30% or DCR=55%, at a type I error rate of 5% (one-sided) based on the Hochberg procedure. For the subgroup of patients on a dose /schedule, the corresponding powers to the two effect sizes are respectively 87% and 97% when the sample size is 40, 76% and 91% when the sample size is 30, and 44% and 62% when the sample size is 15.

Part B ipilimumab-treated enrolled through Amendment 4 (non-randomized)

With 40 patients treated at 10 mg/kg, the study has approximately 92%/98% power to rule out a $\leq 5\%$ spontaneous RR (null hypothesis) when the true RR is 20%/25% at the 5% type I error rate (one-sided). With true RR assumed to be 20%/25%, the corresponding power is 75%/90% when sample size is 30 and 59%/78% when sample size is 20 at Q3W or Q2W.

Part B ipilimumab-refractory enrolled after Amendment 04 (randomized: 10 mg/kg Q3W vs 2 mg/kg Q3W)

With 80 ipilimumab-refractory patients at each dose level, the study has ~85% (or 96%) power to detect a 15% (or 20%) difference in RR between the two doses at the 10%

type I error rate (one-sided) when the RR in the inferior arm is 10%. A p-value of 10% approximately corresponds to a 7% empirical difference in RR.

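### In the ipilimumab-refractory cohort, dose is associated with amendment of enrolment (25:49, then 58:41), and the dose comparison is not stratified by amendment

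*Combined protocol and SAP*

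**What the plan says.** Section 1.5 builds the refractory cohort in two steps: "With Amendment 05, 60 ipilimumab-refractory patients will be enrolled", and then "With Amendment 06, the ipilimumab-refractory cohort will enroll an additional 100 patients for a total of 160 patients". The cohort is to be randomised, up to 80 per dose, "in a 1:1 fashion, manually by the Sponsor, based on a computer-generated allocation schedule". That ratio is given for the whole cohort. No ratio is given for either amendment alone, and no stratification factor is named.

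Table 2-1 in section 2.4.3 gives counts by amendment. Under Amendment 05 it shows "Ipilimumab refractory at 10 mg/kg (Q3W) N=25" and "Ipilimumab refractory at 2 mg/kg (Q3W) N=49". Under Amendment 06 it shows 58 at 10 mg/kg and 41 at 2 mg/kg. The row totals are 83 and 90.

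Section 3.5.7 powers a single randomised comparison of all refractory patients enrolled after Amendment 04: "With 80 ipilimumab-refractory patients at each dose level", about 85% (or 96%) power for a 15-point (or 20-point) difference in RR. Section 3.5.6 sets between-dose tests at 20% two-sided, that is 10% one-sided. Section 3.5.5.1 leaves the method of between-treatment comparison open. The only Part B dose or schedule comparison with a stratified analysis is the 10 mg/kg Q3W versus Q2W cohort, stratified by ipilimumab history (section 3.5.7).

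**The concern.** The overall totals look balanced and hide opposite imbalances in the two periods. A patient on 2 mg/kg is much more likely than one on 10 mg/kg to have been enrolled under Amendment 05. If response differed between periods, for instance through sites or case mix, an unstratified comparison would credit part of that difference to dose. The error could create a dose effect or mask one.

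The dose contrast serves dose selection (section 3.5.9 ties interim looks at this cohort to planning phase 2 studies). Section 3.1.3 also cites a randomised 2 versus 10 mg/kg Q3W comparison labelled KEYNOTE-001 B2 as showing a flat dose response. B2 is not defined in the document, but the refractory cohort is the only randomised 2 versus 10 mg/kg comparison described in Part B.

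**Working it through.** **Plan's power figure.** With 80 per arm, one-sided 10% and Fisher's exact test by full enumeration, power is 85.5% for 10% vs 25% and 96.3% for 10% vs 30%. The stated 85% and 96% are reproduced.

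**Association of dose with period** (counts from Table 2-1)

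| | 10 mg/kg | 2 mg/kg | Share on 10 mg/kg | Exact p against 1:1 |
|---|---|---|---|---|
| Amendment 05 | 25 | 49 | 25/74 = 33.8% | 0.007 |
| Amendment 06 | 58 | 41 | 58/99 = 58.6% | 0.11 |
| Total | 83 | 90 | 83/173 = 48.0% | 0.65 |

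The odds ratio of dose by amendment is (25×41)/(49×58) = 0.36, Fisher p=0.0013. The share from Amendment 05 is 25/83 = 30.1% at 10 mg/kg and 49/90 = 54.4% at 2 mg/kg, a gap of 24.3 points.

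**Bias of the crude difference.** With no dose effect, the expected crude RR difference (10 minus 2 mg/kg) is 0.243 × (RR under Amendment 06 − RR under Amendment 05). The documents give no RR by amendment, so the gaps below are assumptions. RR is set at 20% under Amendment 05 and is higher under Amendment 06.

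The one-sided 10% threshold is 1.28 × √[p(1−p)(1/83+1/90)], with p the pooled RR, (74×RR05 + 99×RR06)/173. For a 5-point gap, p = 22.9% and the threshold is 8.2 points. Error rates are for the crude z test without continuity correction, by enumeration.

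| Assumed gap | Bias | Threshold | One-sided error in direction of bias (nominal 10%) | Two-sided error (nominal 20%) |
|---|---|---|---|---|
| 5 points | 1.2 | 8.2 | 14% | 21% |
| 10 points | 2.4 | 8.5 | 18% | 23% |
| 15 points | 3.6 | 8.8 | 23% | 26% |

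With RR 25% in both periods the one-sided error is 10.1%: no gap, no bias.

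The 7-point difference that section 3.5.7 equates with p=10% belongs to its own scenario, an inferior-arm RR of 10%. It is not the comparator for a base RR of 20%.

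**Cost of stratifying.** Mantel-Haenszel information is the sum over strata of n₁n₂/n:
- Stratified by amendment: 25×49/74 + 58×41/99 = 16.6 + 24.0 = 40.6
- Planned 80:80: 80×80/160 = 40.0
- Actual totals, unstratified: 83×90/173 = 43.2

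In simulation the stratified Cochran-Mantel-Haenszel (CMH) test has about 90% power for 10% vs 25% and 98% for 10% vs 30%. The exact z test at 80:80, also without continuity correction, gives the same 90% and 98%. The CMH test held its one-sided 10% error at every period gap tried.

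**The case against.** **No contradiction with 1:1 is shown.** A reader might infer from 25:49 that randomisation failed. The documents do not support this: the ratio is stated for the 160-patient cohort, and 83:90 fits it. The p=0.007 tests a ratio for Amendment 05 that is nowhere stated. The counts also fit 1:2 and then 3:2 (p=1.00 and p=0.84), which on the planned 60 and 100 gives 20:40 and 60:40, hence 80:80. A deliberate change of ratio is only an inference, but it would itself call for stratification by period.

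**The counts may be wrong.** This stands. The refractory rows add across (25+58=83, 49+41=90), but Amendment 05 shows 25+49=74 against 60 planned. The Part B rows sum to 58+42+22+83+90+147=442 against 564 enrolled in section 1.5. Some neighbouring Part B cells differ from the training-set counts in section 3.5.5.4, for example 17 against 22 for ipilimumab-naïve patients at 10 mg/kg Q3W.

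**No period effect is shown.** This stands too. Section 2.2 lists one set of refractory criteria for Amendments 05 to 08, and nothing reports a shift in response, sites or case mix.

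**The stakes are limited.** A reader might take the dose contrast as a primary hypothesis because refractory melanoma appears in the primary objectives. Those objectives concern RR in the population and in its PD-L1 subset, and section 3.5.7 tests each dose against a fixed 10%. The between-dose contrast is separate. Enrolment is also complete and all ongoing patients now receive one fixed dose, so stratifying now is a re-analysis.

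**Excluding Amendment 05 patients is not warranted.** Nothing shows that any were assigned off schedule. If they were randomised at another ratio, exclusion would discard valid data.

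**Conclusion.** The point holds as a conditional one. If Table 2-1 is right, dose and amendment of enrolment are clearly associated, and the plan does not stratify for it. The confounding is partial: bias is about a quarter of any RR gap between periods, so 1.2 to 3.6 points for assumed gaps of 5 to 15 points, with the two-sided 20% error rising to between about 21% and 26%. These sizes rest on assumed gaps and a base RR of 20%.

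The documents do not show that the dose comparison is in fact biased. Stratification is sufficient protection only if allocation was random within each amendment, which the sponsor should confirm. This is a free improvement.

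**What to change.** 1. Verify the refractory counts in Table 2-1 against the allocation records and correct them if they are wrong.
2. State the allocation ratio and schedule in force under each amendment.
3. Stratify the refractory 2 versus 10 mg/kg comparisons of RR, PFS and OS by amendment of enrolment, using for example CMH or stratified Miettinen-Nurminen for RR. Report the crude result as a sensitivity analysis and keep all randomised patients in.
4. Record the change, with its timing and reason, in the clinical study report, as section 3.5 requires.

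The cost is a records check, a few lines of SAP text and a re-run. Table 2-1 already classifies patients by amendment, and the information is 40.6 against 40.0 planned, so the planned power is kept. The loss against the unstratified 43.2 is about 6% (1 − 40.6/43.2).

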2.5 LIST OF EFFICACY/PHARMACOKINETIC/IMMUNOGENICITY MEASUREMENTS

The Study Flow Chart (Section 1.7) provides specific details on collection time points. Details of collection procedures are found in the Procedures Manual for this study.

Part A, B, C, D and F

The following evaluations will be performed throughout the course of the study:

- Tumor response assessments by physical examination and tumor imaging by CT or magnetic resonance imaging (MRI), with strong preference for CT.
- Anti-pembrolizumab (MK-3475) antibodies
Note: As of Amendment 10, anti-pembrolizumab (MK-3475) antibodies are no longer being collected.
- PK measurements (for detailed PK profiling in Part A, and for assessment of C_{trough} and terminal half-life in Part B, C, D, and F.
Note: As of Amendment 11, PK samples are no longer being collected (see Section 3.3.2).
- ECOG performance status

Part A

The following evaluations will be performed throughout the course of the study:

- Standard serum tumor markers (if applicable)

The following evaluations will be performed throughout the first 12 months of the study and at the Safety Follow-Up Visit:

- Pharmacodynamic measurements: PD-1 receptor occupancy and modulation of PD-1 receptor function
- Analysis of lymphocyte subpopulations

The following evaluations will be performed throughout the first 6 months of the study:

- Chemokine/cytokine measurements in blood
- Proteomics and RNA signature profiling in blood

Part B, C, D, and F

The following evaluations will be performed up to Week 12 (Q2W) and Week 18 (Q3W):

- Proteomics and RNA signature profiling in blood

The following evaluations will be performed up to Week 8 (Q2W) and Week 9 (Q3W):

- Analysis of lymphocyte subpopulations
- Chemokine/cytokine measurements in blood (Part C)

2.6 LIST OF SAFETY MEASUREMENTS

The following safety evaluations will be performed at baseline and throughout the course of the study:

- Vital signs
- Physical examinations
- Medical history
- Evaluation of AEs
- ECOG performance status
- Laboratory tests: complete blood count (CBC), serum chemistry, pregnancy test (at screening and during study when clinically indicated)
- Thyroid function

Toxicity will be graded and recorded according to NCI CTCAE, version 4.0 (<http://ctep.cancer.gov>).

Routine laboratory tests (e.g., CBC with differential; comprehensive serum chemistry panel; urine and serum β -HCG) will be performed by the local study site laboratory. The other laboratory tests will be performed by a central laboratory. Patient treatment and overall management decisions will be based on local laboratory data. Details regarding the amount of blood drawn for testing to be conducted by a central laboratory are provided in the Procedures Manual.

2.7 STATISTICAL ANALYSIS PLAN SUMMARY

Key elements of the statistical analysis plan are summarized below; details are provided in Section 3.5 of the protocol. In particular, details on predictive biomarker analyses are provided in Section 3.5.5.4, sample size and power calculations are provided in Section 3.5.7, and interim analyses are provided in Section 3.5.9.

2.7.1 Efficacy Analyses

Analysis populations

The primary efficacy analyses will be based on the Full Analysis Set (FAS) population. Patients with measurable disease at baseline, which is defined separately under investigator evaluation and central review, who received at least one dose of study treatment will be included in the FAS population. Analyses of PFS and OS are based on the APaT population that consists of all patients who received at least 1 dose of study treatment.

Efficacy endpoints and analysis methods

RR and DCR as assessed per irRC by investigators will serve as primary efficacy endpoints for the ipilimumab-naïve population treated at 10 mg/kg in Part B enrolled through Amendment 4 for internal decision purposes, and the study in this population is considered positive (i.e., demonstration of proof-of-concept) if the outcome in either endpoint is positive. A 95% confidence interval along with a one-sided p-value for testing the null hypothesis based on the binomial distribution will be provided for each for the two primary endpoints: overall RR and overall DCR.

The primary endpoint is RR to demonstrate the anti-tumor activity of pembrolizumab (MK-3475) in all study populations. The primary measure for assessment of tumor response is based on RECIST 1.1 by blinded central reviewers and the secondary measure is based on irRC by investigators. DCR, response duration and PFS based on both irRC and RECIST 1.1, and OS will serve as secondary endpoints. A 95% confidence interval for RR will be provided for each population and by dose/schedule as applicable. Although DCR is not the primary endpoint, similar analyses will also be provided. In addition, Kaplan-Meier plots and descriptive statistics of progression-free-survival (PFS) and overall survival (OS) will be provided. Further, in order to adjust for short follow-up, Kaplan-Meier plot and descriptive statistics of time-to-response will be provided whereas the Kaplan-Meier estimate of cumulative response rate at the longest follow-up time-point will serve as an estimate of the overall response rate. Response rate based on patients with at least 28 weeks of follow-up will also be provided as an approximate of the overall response rate. Descriptive statistics will also be provided for analysis of response duration and tumor volumetric change. Between-treatment comparisons will be conducted for all efficacy endpoints as appropriate to investigate the dose/schedule difference.

2.7.2 Safety Analyses

The All Patients as Treated (APaT) population will be used for the analysis of safety data in this study. The APaT population consists of all patients who received at least 1 dose of study treatment.

In order for a patient to be considered evaluable for the analysis of DLT, the patient must have either had a DLT in Cycle 1 or had received at least 90% of the prescribed dose of

pembrolizumab (MK-3475) in Cycle 1 and completed all safety evaluations up to and including at least 28 days after the first administration of pembrolizumab (MK-3475) without experiencing a DLT. A patient without a DLT will be replaced if he/she did not adequately complete the evaluation period associated with the first cycle of study therapy (i.e., discontinued prematurely due to a reason unrelated to study therapy) or if that patient received <90% of the prescribed dose.

3. PROTOCOL DETAILS

3.1 BACKGROUND/RATIONALE

3.1.1 Background

The importance of intact immune surveillance in controlling outgrowth of neoplastic transformation has been known for decades [1]. Accumulating evidence shows a correlation between tumor-infiltrating lymphocytes (TILs) in cancer tissue and favorable prognosis in various malignancies [21-58]. In particular, the presence of CD8+ T-cells and the ratio of CD8+ effector T-cells / FoxP3+ regulatory T-cells seems to correlate with improved prognosis and long-term survival in solid malignancies such as ovarian, colorectal and pancreatic cancer, hepatocellular carcinoma, malignant MEL and RCC. TILs can be expanded *ex vivo* and re-infused, inducing durable objective tumor responses in cancers such as MEL [59, 60].

The PD-1 receptor-ligand interaction is a major pathway hijacked by tumors to suppress immune control. The normal function of PD-1, expressed on the cell surface of activated T-cells under healthy conditions, is to down-modulate unwanted or excessive immune responses, including autoimmune reactions. PD-1 (encoded by the gene *Pdcd1*) is an Ig superfamily member related to CD28 and CTLA-4 which has been shown to negatively regulate antigen receptor signaling upon engagement of its ligands (PD-L1 and/or PD-L2) [61, 62]. The structure of murine PD-1 has been resolved [63]. PD-1 and family members are type I transmembrane glycoproteins containing an Ig Variable-type (V-type) domain responsible for ligand binding and a cytoplasmic tail which is responsible for the binding of signaling molecules. The cytoplasmic tail of PD-1 contains 2 tyrosine-based signaling motifs, an immunoreceptor tyrosine-based inhibition motif (ITIM) and an immunoreceptor tyrosine-based switch motif (ITSM). Following T cell stimulation, PD-1 recruits the tyrosine phosphatases SHP-1 and SHP-2 to the ITSM motif within its cytoplasmic tail, leading to the dephosphorylation of effector molecules such as CD3 ζ , PKC θ and ZAP70 which are involved in the CD3 T cell signaling cascade [62, 64-66]. The mechanism by which PD-1 down modulates T cell responses is similar to, but distinct from that of CTLA-4 as both molecules regulate an overlapping set of signaling proteins [5, 67]. PD-1 was shown to be expressed on activated lymphocytes including peripheral CD4+ and CD8+ T-cells, B cells, T regs and Natural Killer cells [68, 69]. Expression has also been shown during thymic development on CD4-CD8- (double negative) T-cells as well as subsets of macrophages and dendritic cells [70]. The ligands for PD-1 (PD-L1 and PD-L2) are constitutively expressed or can be induced in a variety of cell types, including non-hematopoietic tissues as well as in various tumors [2-5]. Both ligands are type I transmembrane receptors containing both IgV- and IgC-like domains in the extracellular region and contain short cytoplasmic regions with no known signaling motifs. Binding of either PD-1 ligand to PD-1 inhibits T cell activation triggered through the T cell receptor. PD-L1 is expressed at low levels on various non-hematopoietic tissues, most notably on vascular endothelium, whereas PD-L2 protein is only detectably expressed on antigen-presenting cells found in lymphoid tissue or chronic inflammatory environments. PD-L2 is thought to control immune T cell activation in lymphoid organs, whereas PD-L1 serves to dampen unwarranted T cell function in

peripheral tissues [5]. Although healthy organs express little (if any) PD-L1, a variety of cancers were demonstrated to express abundant levels of this T cell inhibitor. High expression of PD-L1 on tumor cells (and to a lesser extent of PD-L2) has been found to correlate with poor prognosis and survival in various cancer types, including RCC [6], pancreatic carcinoma [7], hepatocellular carcinoma [8], and ovarian carcinoma [9]. Furthermore, PD-1 has been suggested to regulate tumor-specific T cell expansion in patients with MEL [10].

The observed correlation of clinical prognosis with PD-L expression in multiple cancers suggests that the PD-1/PD-L1 pathway plays a critical role in tumor immune evasion and should be considered as an attractive target for therapeutic intervention.

Therapeutic studies in mouse models have shown that administration of antibodies blocking PD-1/PD-L1 interaction enhances infiltration of tumor-specific CD8⁺ T-cells and leads ultimately to tumor rejection, either as a mono-therapy or in combination with other treatment modalities. Anti-mouse PD-1 or anti-mouse PD-L1 antibodies have demonstrated anti-tumor responses as a mono-therapy in models of squamous cell carcinoma, pancreatic carcinoma, MEL and colorectal carcinoma. Blockade of the PD-1 pathway effectively promoted CD8⁺ T cell infiltration into the tumor and the presence of IFN- γ , granzyme B and perforin, indicating that the mechanism of action involved local infiltration and activation of effector T cell function *in vivo* [7, 11-15]. In addition, the combination of gemcitabine and anti-PD-L1 mAb demonstrated synergy in the rejection of pancreatic mouse tumors [7]. In-house experiments have confirmed the *in vivo* efficacy of PD-1 blockade as a mono-therapy as well as in combination with chemotherapy in syngeneic mouse tumor models (see the IB).

